12.2.5. Exploratory Analyses

The methodology described above for the primary analysis will be repeated using data from each participant individually.

Within the occluded inspiration and end-expiratory breath holds (representing obstructive and central apneas, respectively), we will categorize each signal as being above or below a threshold. Each period will be identified as a true positive for obstructive apnea (esophageal manometry scored as occluded inspiration and DreamKit signal above the threshold), true negative (esophageal manometry scored as breath-hold and DreamKit signal below the threshold), false positive (esophageal manometry signal scored as breath hold but DreamKit signal above the threshold), or false negative (esophageal manometry signal scored as occluded inspiration but DreamKit signal below the threshold). This will allow us to calculate the sensitivity, specificity, and area under the ROC curve for the ability of the DreamKit signal to identify obstructive apnea events. The threshold for calculating sensitivity and specificity will be 10% of the baseline amplitude derived from normal (relaxed) breathing. This threshold corresponds to a proportional change in respiratory effort for an apneic event that requires a 90% reduction of flow amplitudes as compared to the baseline respiration.

Document ID:	SRC_SLE_Sparkle EP 2_2021_11315	Document title:		Classification:	Confidential
Modified:	12 May 2021	Clinical Investigation Protocol ICH E6 Aligned			
Version:	1	User Tool ID:	16.2.6UserTool0004		
Status:	FINAL	User Tool Version Date	5June2019	Page:	28

Within the increased inspiratory/expiratory resistance and shallow breathing periods (representing obstructive and central hypopneas), we will calculate the area under the ROC curve which will provide an aggregate assessment of agreement between the two respiratory effort signals across all possible thresholds. Unlike apneas, the classification of hypopneas as obstructive or central is not based on the presence or absence of respiratory effort (AASM scoring criteria; Version 2.6), and therefore we will not categorize each breathing period on the basis of a respiratory effort threshold.

The respiratory rate will be extracted from each breathing condition except breath holds, and we will provide a Bland-Altman analysis of respiratory rate between the esophageal pressure signal and the DreamKit device.

Finally, to evaluate the phase relationship between the esophageal pressure and DreamKit signals, the peaks in the cross-correlation function will be used to estimate the average phase shift between the two effort signals. All manually scored epochs of relaxed breathing, slow breathing, fast breathing, occluded inspiration, increased inspiratory resistance, increased expiratory resistance, and unresisted shallow breathing will be used for this analysis.

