4.2. Exploratory Objectives

Our exploratory objectives are:

- To repeat the analysis for the primary objective for each participant individually.
- Within the periods of occluded inspiration (representing obstructive apneas) and end-expiratory breath-holds (representing central apneas), to categorize each respiratory effort signal as being above or below a threshold of 10% of the baseline amplitude derived from normal (relaxed) breathing, in order to calculate sensitivity, specificity, and the area under the receiver operating characteristic (ROC) curve for the detection of obstructive events (overall and for each participant individually).
- Within the periods of increased inspiratory and expiratory resistance (representing obstructive hypopneas) and unresisted shallow breathing (representing central hypopneas), to calculate the area under the ROC curve in order to assess the agreement between the respiratory effort signals across all possible thresholds.

Document ID:	SRC_SLE_Sparkle EP 2_2021_11315	Document title:		Classification:	Confidential
Modified:	12 May 2021	Clinical Investigation Protocol ICH E6 Aligned			
Version:	1	User Tool ID:	16.2.6UserTool0004		
Status:	FINAL	User Tool Version Date	5June2019	Page:	13

- To compare the number of breaths/minute between esophageal manometry and the DreamKit device during relaxed breathing, fast breathing, slow breathing, occluded inspiration, increased inspiratory resistance, increased expiratory resistance, and unresisted shallow breathing.
- To evaluate the phase relationship between esophageal manometry and the DreamKit device during relaxed breathing, fast breathing, slow breathing, occluded inspiration, increased inspiratory resistance, increased expiratory resistance, and unresisted shallow breathing.

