Using the timing information noted during data collection, an analyst blinded to the DreamKit data will score the esophageal pressure data files in order to identify the periods of occluded inspiration, end-expiratory breath-holds, increased inspiratory resistance, increased expiratory resistance, shallow breathing, slow respiration, fast respiration, and relaxed breathing. Periods of poor pressure signal quality will be excluded from analyses, such as artifact caused by movement, swallowing, or sensor displacement. An independent analyst will then import the DreamKit signal and ensure that the two data sources (Alice 6 and DreamKit) are synchronized following the procedures above. Periods where the DreamKit device indicates poor effort data quality by means of channel fail events will be excluded from analyses.

Follow-up phone call

A follow-up phone call will be placed 1-2 days after completion Visit 2, in order to assess any AEs that may have become apparent in the intervening period.

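### Sections 4.2 and 12.2.5 announce a 10% threshold for each effort signal, but the 2x2 table thresholds only DreamKit and takes its reference from manoeuvre scoring with no stated esophageal amplitude criterion

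*Combined protocol and SAP*

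**What the plan says.** Section 4.2 sets the exploratory aim, within the occluded-inspiration and breath-hold periods, "to categorize each respiratory effort signal as being above or below a threshold of 10% of the baseline amplitude derived from normal (relaxed) breathing". Sensitivity, specificity and ROC area then follow "for the detection of obstructive events (overall and for each participant individually").

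Section 12.2.5 starts in the same way: "we will categorize each signal as being above or below a threshold". Its cell definitions, however, bring in only one thresholded signal. A period is a "true positive for obstructive apnea (esophageal manometry scored as occluded inspiration and DreamKit signal above the threshold") or a "true negative (esophageal manometry scored as breath-hold and DreamKit signal below the threshold"). The false-positive and false-negative cells follow the same pattern. The cut-off is stated once: "The threshold for calculating sensitivity and specificity will be 10% of the baseline amplitude derived from normal (relaxed) breathing".

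Section 9.1.3 (Data processing) explains where the scored label comes from: "Using the timing information noted during data collection, an analyst blinded to the DreamKit data will score the esophageal pressure data files", so as to identify the periods belonging to each manoeuvre. Periods with poor pressure signal are excluded, as are periods in which DreamKit flags a channel failure. No amplitude rule for the label is given.

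**The concern.** Two sections announce an esophageal above/below-10% category, and no cell of the table uses it. An analyst working from 4.2 and an analyst working from the 12.2.5 cells could build different tables from the same recordings. Section 12.2.5 is also inconsistent within itself, since it opens with each signal and ends with one.

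The difference matters when a manoeuvre is recorded cleanly but performed imperfectly. The exclusions in 9.1.3 concern signal quality, so nothing stated removes or reclassifies a hold in which the participant makes an effort, or an occlusion in which the participant makes almost none. The minimal pressure change asked for during holds is an unquantified coaching aim. The numeric pressure target in 9.1.3 covers only the resistance conditions. If such a hold keeps its label, a DreamKit signal that correctly follows the effort becomes a false positive. A weak occlusion that DreamKit correctly shows as low effort becomes a false negative.

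Section 5.2.2 argues for comparison with esophageal pressure as the gold standard, section 5.2.3 calls presence or absence of effort the relevant question in apneas, and the intended use in 4.3 includes classifying events as central, mixed or obstructive. This table is the only planned sensitivity and specificity analysis of that distinction. Section 12.2.1 plans no sensitivity analyses that would show device error and manoeuvre failure separately.

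**Working it through.** The plan gives no expected sensitivity, specificity or precision for this analysis, so there is no figure to reproduce. The check is a comparison of texts followed by an illustrative count.

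**Which signal is thresholded, and what is the reference?**

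| Place | Signals thresholded at 10% | Reference for the table |
|---|---|---|
| 4.2 | Each effort signal | Not named; the target is obstructive events |
| 12.2.5, opening | Each signal | Not named |
| 12.2.5, four cells | DreamKit only | Scored manoeuvre on the esophageal file |
| 9.1.3, Data processing | None | Label from blinded scoring with timing notes; no amplitude rule |

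**Number of periods.** From 9.1.3 there are ten breath holds and five occlusions per participant. From 12.1 there are ten evaluable participants. The maximum is 10 x 10 = 100 holds (label-negative) and 10 x 5 = 50 occlusions (label-positive), 150 in all before quality exclusions.

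**Assumed discordance.** Let f be the share of scored holds with esophageal amplitude above 10% of baseline, and g the share of scored occlusions below it. The documents give neither. I use 0% to 20% as an assumed range.

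*Case A: DreamKit agrees exactly with the esophageal 10% class.* Against that class, sensitivity and specificity are both 1.00. Against the scored label:

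- sensitivity = 50(1 - g)/50 = 1 - g
- specificity = 100(1 - f)/100 = 1 - f

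*Case B: DreamKit agrees exactly with the scored label.* Against the label, both are 1.00. Against the esophageal class:

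- sensitivity = 50(1 - g) / [50(1 - g) + 100f]
- specificity = 100(1 - f) / [100(1 - f) + 50g]

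At f = g = 10%, case B gives 45/(45 + 10) = 0.818 and 90/(90 + 5) = 0.947.

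| f = g (assumed) | Case A, label reference: sens / spec | Case B, esophageal-class reference: sens / spec |
|---|---|---|
| 0% | 1.00 / 1.00 | 1.00 / 1.00 |
| 5% | 0.95 / 0.95 | 0.905 / 0.974 |
| 10% | 0.90 / 0.90 | 0.818 / 0.947 |
| 20% | 0.80 / 0.80 | 0.667 / 0.889 |

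The two references give the same table for any device behaviour only when f = g = 0. Otherwise either choice can look better or worse, depending on what DreamKit follows.

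**The case against.** The strongest reply is that the label is a sound reference. It comes from a reading of the gold-standard trace by an analyst who does not see DreamKit, and both sections name obstructive events as the target. For that target a scored manoeuvre is coherent, and the 12.2.5 cells can be carried out as written. The primary ICC already tests whether DreamKit amplitude follows esophageal amplitude in these same periods. Participants practise, are coached and are watched on the esophageal channel, so failed manoeuvres may be few. The analysis is exploratory and has no performance target.

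Most of this stands, and it rules out three stronger readings that a reader might infer:

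- *That sensitivity and specificity ignore esophageal pressure and measure only compliance with the instruction.* The label is scored on the esophageal file, with timing notes as an aid. Nothing says a hold with visible effort must still be scored as a hold. What is missing is a stated amplitude criterion.
- *That 4.2 makes thresholded esophageal amplitude the truth, so a perfect device would score 100% under 4.2.* Section 4.2 has both signals categorised but never names the reference. The 1.00 / 1.00 in case A holds only if the esophageal class is chosen.
- *That the breath-hold quartiles in 9.1.3 (-2.9 to 2.0 mmHg) show how often holds fail.* They come from a previous study and describe change from normal breathing. Without a baseline amplitude they cannot be converted to a share above 10% of baseline.

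The reply does not remove the mismatch between the announced category and the cells, nor supply a rule for cleanly recorded but failed manoeuvres. The pooled ICC does not show which table errors come from the device and which from the manoeuvre.

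**Conclusion.** The point holds as an inconsistency with a practical consequence for an exploratory analysis. The esophageal 10% category is announced in both sections and used in neither table definition. The resulting sensitivity and specificity are relative to a blinded manoeuvre label without a stated amplitude criterion, so manoeuvre failure can be charged to DreamKit.

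The size cannot be determined from the documents. The values in the table above rest on assumed f and g, on all 150 planned periods being usable, on failed manoeuvres keeping their label, and on idealised device behaviour. If every hold is below threshold and every occlusion above it, there is no effect. The primary endpoint and its hypothesis are not touched. The change is still worth making before analysis, because the choice of reference can move the results in either direction.

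**What to change.** 1. Make 4.2 and 12.2.5 agree by naming the reference for the 2x2 table. If it is the scored manoeuvre, say that only DreamKit is thresholded for that table, and state any amplitude criterion used in scoring. If it is the esophageal class, rewrite the four cell definitions.
2. Whichever is named, also classify each hold and occlusion from its esophageal amplitude with the same 10%-of-baseline rule, and state how amplitude is summarised over a period, identically for both signals.
3. Report DreamKit against the esophageal class beside DreamKit against the manoeuvre label, overall and by participant.
4. Report the number of holds and of occlusions in which label and esophageal class differ. This replaces the assumed f and g with observed values.

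The cost is SAP wording and one extra cross-tabulation. Section 12.2.4 already extracts esophageal amplitudes for these periods, and the relaxed breathing needed for the baseline is already recorded and scored. No new data are needed.

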12.3. Safety Analyses

Safety evaluations will be performed by recording clinical AEs at the time originally reported, and they will be followed at regular intervals until resolution. AEs will be provided in data listings.

12.4. Planned Interim Analyses

There are no planned interim analyses.

12.5. Missing Unused and Spurious Data

Imputations methods will not be employed in this study.

12.6. Deviations from the Statistical Analysis Plan

Any deviations from the original statistical plan will be noted in the analysis report.

13. OPERATIONAL CONSIDERATIONS

13.1. Regulatory and Ethical Considerations

13.1.1. Informed Consent Process

Participants will be asked to complete the consent form prior to any study procedures, including screening for eligibility.

Document ID:	SRC_SLE_Sparkle EP 2_2021_11315	Document title:	Document title:		Confidential
Modified:	12 May 2021	Clinical Investigation Protocol ICH E6 Aligned			
Version:	1	User Tool ID:	16.2.6UserTool0004		
Status:	FINAL	User Tool Version Date	5June2019	Page:	29

In obtaining and documenting informed consent, the investigator must comply with applicable regulatory requirements (e.g., 45 CFR Part 46, 21 CFR Part 50, 21 CFR Part 56) and should adhere to ICH GCP. Prior to the beginning of the trial, the investigator should have the IRB's written approval for the protocol and the written informed consent form(s) and any other written information to be provided to the participants.

Study participation is voluntary. Potential subjects, and/or their legal representatives, will be given the most current IRB-approved consent form to read. They shall be provided ample time for review and an opportunity to ask questions about the study. If they agree to participate, they shall sign the consent form and be given a copy of the signed document for their records. Each of these actions/steps will be documented. Only after informed consent has been obtained, may the remaining study procedures begin.

13.1.2. Consent Procedures and Documentation

Informed consent is a process that is initiated prior to the individual's agreeing to participate in the study and continues throughout the individual's study participation. Consent forms will be IRB-approved and the participant will be asked to read and review the document. The investigator will explain the research study to the participant and answer any questions that may arise. A verbal explanation will be provided in terms suited to the participant's comprehension of the purposes, procedures, and potential risks of the study and of their rights as research participants. Participants will have the opportunity to review the written consent form carefully and ask questions prior to signing. The participants should have the opportunity to discuss the study with their family or surrogates or think about it prior to agreeing to participate. Participants must be informed that participation is voluntary and that they may withdraw from the study at any time, without prejudice. A copy of the informed consent document will be given to the participants for their records. The informed consent process will be conducted and documented in the source document (including the date), and the form signed, before the participant undergoes any study-specific procedures. The rights and welfare of the participants will be protected by emphasizing to them that the quality of their medical care will not be adversely affected if they decline to participate in this study.

13.1.3. Study Discontinuation and Closure

Although there are no pre-determined criteria for study closure, the study may be temporarily suspended or prematurely terminated if there is sufficient reasonable cause. If the study is prematurely terminated or suspended, the PI will promptly inform study participants, the IRB, and Sponsor, and will provide the reason(s) for the termination or suspension. Study participants will be contacted, as applicable, and be informed of changes to study visit schedule.

Circumstances that may warrant termination or suspension include, but are not limited to:

- Determination of unexpected, significant, or unacceptable risk to participants;
- Insufficient compliance to protocol requirements;

Document ID:	SRC_SLE_Sparkle EP 2_2021_11315	Document title:	Document title:		Confidential
Modified:	12 May 2021	Clinical Investigation Protocol ICH E6 Aligned			
Version:	1	User Tool ID:	16.2.6UserTool0004		
Status:	FINAL	User Tool Version Date	5June2019	Page:	30

Data that are not sufficiently complete and/or evaluable.

Study may resume once concerns about safety, protocol compliance, and data quality are addressed, and satisfy the Sponsor, IRB and/or FDA.

13.1.4. Confidentiality and Privacy

Participant confidentiality and privacy is strictly held in trust by the participating investigators, their staff, and the Sponsor. The study protocol, documentation, data, and all other information generated will be held in strict confidence. No information concerning the study or the data will be released to any unauthorized third party without prior written approval of the Sponsor.

All research activities will be conducted in as private a setting as possible.

The study monitor, other authorized representatives of the Sponsor, representatives of the IRB, regulatory agencies or pharmaceutical company supplying study product may inspect all documents and records required to be maintained by the investigator, including but not limited to, medical records (office, clinic, or hospital) and pharmacy records for the participants in this study. The clinical study site will permit access to such records.

Each study participant's contact information will be securely stored at each clinical site for internal use during the study. At the end of the study, all records will continue to be kept in a secure location for as long a period as dictated by the reviewing IRB, institutional policies, or Sponsor requirements.

Study participant research data for statistical analysis and scientific reporting will be transmitted to and stored by the Sponsor. This will not include the participant's contact or identifying information. Rather, individual participants and their research data will be identified by a unique study identification number. The study data entry and study management systems used by clinical sites and by the Sponsor research staff will be secured and password protected. At the end of the study, all study databases will be deidentified and archived at the Sponsor.

13.2. Future Use of Stored Specimens and Data

Data collected for this study will be analyzed and stored at the Sponsor, where it may be used for future research. During the conduct of the study, an individual participant can choose to withdraw consent to have biological specimens stored for future research. However, withdrawal of consent with regard to data storage may not be possible after the study is completed.

13.3. Safety Oversight

Safety oversight is the responsibility of the PI. It has been determined that a Safety Monitoring Committee, Data and Safety Monitoring Board, Safety Assessment Committee and/or an Independent Safety Monitor is not required for this study.

Document ID:	SRC_SLE_Sparkle EP 2_2021_11315	Document title:		Classification:	Confidential
Modified:	12 May 2021	Clinical Investigation Protocol ICH E6 Aligned			
Version:	1	User Tool ID:	16.2.6UserTool0004		
Status:	FINAL	User Tool Version Date	5June2019	Page:	31

13.4. Clinical Monitoring

This study will be monitored using a risk-based monitoring approach. It will ensure that documents used to originally record subject data (source documents) are maintained, and to verify that transcribed data are accurately reflected on the study CRFs. All study documentation must be made available for review by the Sponsor or its designees as well as regulatory agencies.

13.5. Quality Assurance and Quality Control

The clinical site will perform internal quality management of study conduct, data collection, documentation and completion.

Quality control (QC) procedures will be implemented beginning with the data entry system and data QC checks that will be run on the database will be generated. Any missing data or data anomalies will be communicated to the site(s) for clarification/resolution.

The investigational site will provide direct access to all trial related sites, source data/documents, and reports for the purpose of monitoring and auditing by the Sponsor, and inspection by local and regulatory authorities.

13.5.1. Data Handling and Record Keeping

The site will maintain appropriate medical and research records for this trial, in compliance with ICH GCP and regulatory and institutional requirements for the protection of confidentiality of participants.

13.5.2. Data Collection and Management Responsibilities

Data collection is the responsibility of the staff at the site under the supervision of the site investigator. The investigator is responsible for ensuring the accuracy, completeness, legibility, and timeliness of the data reported.

All source documents should be completed in a neat, legible manner to ensure accurate interpretation of data.

Hardcopies of the study visit worksheets will be provided for use as source document worksheets for recording data for each participant enrolled in the study. Data recorded in the CRF derived from source documents should be consistent with the data recorded on the source documents.

Clinical data (including AEs), concomitant medications, and expected adverse reactions data) and clinical laboratory data will be entered into a 21 CFR Part 11-compliant data capture system provided by the Sponsor. The data system includes password protection and internal quality checks, such as automatic range checks, to identify data that appear inconsistent, incomplete, or inaccurate. Clinical data will be entered directly from the source documents.

Document ID:	SRC_SLE_Sparkle EP 2_2021_11315	Document title:		Classification:	Confidential
Modified:	12 May 2021	Clinical Investigation Protocol ICH E6 Aligned			
Version:	1	User Tool ID:	16.2.6UserTool0004		
Status:	FINAL	User Tool Version Date	5June2019	Page:	32

